### **5.3.6 Assessments after Completion of CRT**

1. Office FOE and CT neck (with IV contrast) and CT chest (or CXR) at 8, 12, 18, 24, 30, 36, 42, 48, 54, and 60 months (+/- 1 month) after completion of CRT [FOE will be conducted as standard of care after 12 months of follow-up, so they will occur at some, but not all, of the long-term follow-up visits]
2. Documentation of presence of PEG tube or tracheostomy tube at the same monitoring intervals.
3. Documentation of weight (Kg) at the same monitoring intervals.
4. QOL assessments at the same monitoring intervals.
5. Study Lab collection of 3 green top tubes for PBMC at 4 months (+/- 1 month) after completion of adjuvant treatment (4 months post step 3).

## **5.4 Toxicity and Response Evaluations**

All patients who receive any study treatment are evaluable for toxicity. Patients are evaluated from first receiving study treatment until a 30-day follow up after the conclusion of treatment or death.

All patients are evaluable for disease response unless they discontinue treatment due to adverse event(s), patient withdrawal, or early death prior to completion of the disease

assessment at the end of Step 1(neoadjuvant treatment) and have not had any disease assessment.

## **5.5 General Concomitant Medication and Supportive Care Guidelines**

While taking palbociclib, patients should be instructed to avoid food or drugs that are known strong CYP3A4 inhibitors or inducers (moderate CYP3A4 inhibitors or inducers are okay). Patients should also refrain from the use of proton pump inhibitors; if needed, alternative antacid therapies may be used including H2-receptor antagonists, and locally acting antacids. H2-receptor antagonists should be administered with a staggered dosing regimen (twice daily). The dosing of palbociclib should occur at least 10 hours after the H2-receptor antagonist dose and 2 hours before the H2-receptor antagonist morning dose. Local antacid should be given at least 2 hours before or 2 hours after palbociclib administration.

Patients should receive full supportive care during the study, including transfusion of blood and blood products and treatment with antibiotics, analgesics, erythropoietin, or bisphosphonates when appropriate.

Anti-emetics (such as prochlorperazine, lorazepam, ondansetron, or other 5-HT3 antagonists) may be administered prophylactically in the event of nausea. Anti-diarrheals, such as loperamide, may be administered as needed in the event of diarrhea.

## **5.6 Women of Childbearing Potential**

Women of childbearing potential (defined as women with regular menses, women with amenorrhea, women with irregular cycles, women using a contraceptive method that precludes withdrawal bleeding, and women who have had a tubal ligation) are required to have a negative serum pregnancy test within 28 days prior to the first dose of palbociclib.

Female and male patients (along with their female partners) are required to use two forms of acceptable contraception, including one barrier method, during participation in the study and for 3 months following the last dose of palbociclib.

If a patient is suspected to be pregnant, all study drugs should be immediately discontinued. In addition, a positive urine test must be confirmed by a serum pregnancy test. If it is confirmed that the patient is not pregnant, the patient may resume dosing.

If a female patient or female partner of a male patient becomes pregnant during therapy or within 28 days after the last dose of palbociclib, the investigator must be notified in order to facilitate outcome follow-up.

## **5.7 Duration of Therapy**

If at any time the constraints of this protocol are considered to be detrimental to the patient's health and/or the patient no longer wishes to continue protocol therapy, the

protocol therapy should be discontinued and the reason(s) for discontinuation documented in the case report forms.

In the absence of treatment delays due to adverse events, treatment may continue for 2 cycles of neoadjuvant palbociclib, 6 weeks of CRT, and 6 cycles of adjuvant palbociclib or until one of the following criteria applies:

- Documented and confirmed disease progression after Step 2. Patients with disease progression after Step 1 should proceed to Step 2.
- Death
- Adverse event(s) that, in the judgment of the investigator, may cause severe or permanent harm or which rule out continuation of study drug
- General or specific changes in the patient's condition render the patient unable to receive further treatment in the judgment of the investigator
- Suspected pregnancy
- Serious non-compliance with the study protocol
- Lost to follow-up
- Patient withdraws consent
- Investigator removes the patient from study
- The Siteman Cancer Center decides to close the study

Patients who prematurely discontinue treatment for any reason will be followed as indicated in the study calendar.

## **5.8 Duration of Follow-up**

Patients will have follow-up visits after the end of treatment at 30-45 days, and will also have visits at 8 months after end of CRT, 12 months after end of CRT, and every 6 months thereafter until 5 years have elapsed since the end of treatment. Patients removed from study for unacceptable adverse events will be followed until resolution or stabilization of the adverse event.

## **6.0 DOSE DELAYS/DOSE MODIFICATIONS**

### **6.1 Dose Modifications for Palbociclib (Steps One and Three)**

Patients will be monitored for toxicity and the dose of palbociclib may be adjusted as indicated in the table below. Dose reduction by 1, and if possible, 2 dose levels will be allowed depending on the type and severity of toxicity encountered. Patients requiring more than 2 dose reductions will be discontinued from the study.

Recommended dose reductions for palbociclib are to decrease the current dose by 25 mg. The lowest dose available is 75 mg. Doses may be held as needed for toxicity resolution during a cycle. Doses omitted for toxicity are not replaced or restored within the same cycle (meaning that the cycle remains 28 days regardless of the number of doses of taken).

If a patient experiences toxicity which has not resolved to grade 2 or lower within two weeks (inclusive of the scheduled off-week), treatment with palbociclib should be permanently discontinued.

### **Palbociclib Dose Modifications Based on Worst Treatment-Related Toxicity in the Previous Cycle**

Worst Toxicity During Previous Cycle	New Dose Level
Grade 4 neutropenia	- Withhold Palbociclib until recover to Grade $\leq$ 2. Resume at the next lower dose.
Grade 4 thrombocytopenia	- Withhold Palbociclib until recover to Grade $\leq$ 2. Resume at the next lower dose.
Grade 3 neutropenia associated with a documented infection or fever $\geq$ 38.5 °C	Withhold Palbociclib until recover to Grade $\leq$ 2. Resume at the next lower dose.
Grade $\geq$ 3 non-hematologic toxicity (includes nausea, vomiting, diarrhea, and hypertension only if persisting despite maximal medical treatment)	Withhold Palbociclib until symptoms resolve to 
 
• Grade <math>\leq</math> 1:
 
• Grade <math>\leq</math> 2 (if not considered a safety risk for the patient)
 
 Resume at the next lower dose.
Delay by > 1 week in receiving the next scheduled dose due to persisting treatment-related toxicities	If recovery to Grade $\leq$ 2 occurs within 2 weeks, continue and decrease by one dose level
Inability to deliver at least 80% of the planned dose of palbociclib due to adverse events possibly related to study treatment	Withhold Palbociclib until recovery to Grade $\leq$ 2. Decrease by one dose level.

#### **6.1.1 Dose Adjustments Due to QTc Prolongation**

Any patients who develops new grade 2 or greater ECG QT corrected interval prolonged at any time during the study will need to have the ECG repeated immediately for confirmation.

Grade 2: no adjustments; continue at same dose level

Grade 3 (reversible cause identified and corrected): withhold treatment until QTc  $\leq$  470 msec, then resume treatment at the same dose level

Grade 3 (no reversible cause identified): withhold treatment until QTc  $\leq$  470 msec, then decrease palbociclib by one dose level

Grade 4: permanently discontinue palbociclib

### 6.1.2 Dose Adjustments Due to Interstitial Lung Disease (ILD)/Pneumonitis

Monitor patients for pulmonary symptoms indicative of ILD/pneumonitis (e.g. hypoxia, cough, dyspnea). In patients who have new or worsening respiratory symptoms and are suspected to have developed ILD/pneumonitis, interrupt palbociclib immediately and evaluate the patient. Permanently discontinue palbociclib in patients with severe ILD or pneumonitis.

## 6.2 Step Two, Cohort 1: Dose Modifications for Cisplatin

### 6.2.1 Peripheral Neuropathy

Grade 0, 1, or 2: no dose modification.

Grade 3 or 4: Hold cisplatin until the event resolves to < grade 3.

### 6.2.2 Ototoxicity

If grade 1 or 2 hearing loss occurs, the risk of additional hearing loss versus the potential benefit of continuing cisplatin chemotherapy should be made. Grade 3 and 4 hearing loss is an indication to discontinue the drug.

### 6.2.3 Kidney Impairment

Calculated Creatinine Clearance	Percent Dose to Give	
≥ 60 mL/min	100%	
	0% (withhold treatment for this cycle and repeat serum creatinine weekly after additional hydration), then for next chemotherapy cycle:	
< 60 mL/min	If CrCl was already < 60 mL/min and is now:	The percent dose to give is:
	> 50 but < 60	80%
	≥ 40 but ≤ 50	50%
< 40	0%	

Please note that dose reduction percentage is calculated by taking off from the original dose and not the previous dose. Creatinine clearance is to be calculated using Cockcroft-Gault.

### 6.2.4 Thrombocytopenia

Nadir of last course	Platelets (Day 1 of each cycle)	
	< 100,000	≥ 100,000

between 50,000 and 100,000	Hold cisplatin	Cisplatin = 100%
< 50,000 (1 st occurrence)	Hold cisplatin	Cisplatin = 80%
<50,000 (2 nd occurrence)	Hold cisplatin	Cisplatin = 60%

### 6.3 Step Two, Cohort 2: Dose Modifications or Delays for Cetuximab

#### 6.3.1 Dermatologic Adverse Effects

Patients developing dermatologic toxicities while receiving cetuximab should be monitored for the development of inflammatory or infectious sequelae, and appropriate treatment of these symptoms initiated. Dose modifications of any future cetuximab infusions should be instituted in case of severe (grade 3) acneiform rash. Treatment with topical and/or oral antibiotics (minocycline 100 mg bid) should be considered; topical corticosteroids are not recommended.

If a patient experiences severe acneiform rash, cetuximab treatment adjustments should be made according to the following table. In patients with mild and moderate skin toxicity, treatment should continue without dose modification.

#### Cetuximab Dose Modification Guidelines

Grade 3 Acneiform Rash	Cetuximab	Outcome	Cetuximab Dose Modification
1 st occurrence	Delay infusion 1-2 weeks	Improvement	Continue at 250 mg/m 
		No Improvement	Discontinue cetuximab
2 nd occurrence	Delay infusion 1-2 weeks	Improvement	Reduce Dose Level -1
		No Improvement	Discontinue cetuximab
3 rd occurrence	Delay infusion 1-2 weeks	Improvement	Reduce to Dose Level -2
		No Improvement	Discontinue cetuximab
4 th occurrence		Discontinue cetuximab	

#### Cetuximab Dose Levels\*

Starting dose	250 mg/m 
Dose Level -1	200 mg/m 
Dose Level -2	150 mg/m 

\*There will be no dose level reductions below a weekly dose of 150 mg/m^2.

#### 6.3.2 Gastrointestinal Adverse Effects

Antiemetic agents may be administered prior to the administration of cetuximab. Diarrhea will be treated symptomatically with antidiarrheal agents. Should GI toxicity become severe enough to require hospitalization or outpatient IV fluid replacement, all treatment should be discontinued temporarily until the patient's condition improves.

### **6.3.3 Management of Hypersensitivity Reactions**

Mild (grade 1) hypersensitivity reactions (HSRs) characterized by mild pruritus, flushing, rhinitis, rash, and fever are treated with symptom-directed management, including cessation of infusion, administration of diphenhydramine 25 mg IVP (may repeat x2). Vital signs should be monitored every 15 minutes until symptoms resolve. Treatment may be restarted at the same rate at resolution of symptoms.

Moderate (grade 2) HSRs consist of generalized pruritus, flushing, rash, back pain, dyspnea, hypotension, and rigors. The infusion should be stopped, and oxygen should be administered if the patient is experiencing dyspnea. Normal saline 500 mL bolus may be given if the patient is hypotensive (may repeat as needed). Diphenhydramine 50 mg IVP should be administered, followed by hydrocortisone 100 mg IVP followed by meperidine 25 mg IV (for rigors). Vital signs should be monitored every 2 minutes until stable, then every 15 minutes until symptoms resolve. Treatment may be restarted at resolution of symptoms as follows: 8 hour rate for 5 minutes, then 4 hour rate for 5 minutes, the 2 hour rate for 5 minutes until the original rate of infusion is reached.

Severe (grade 3) HSRs are characterized by bronchospasm, generalized urticaria, hypotension, and angioedema. These HSRs should be managed by stopping the infusion and administering: normal saline 500 mL bolus (repeat as needed), epinephrine (1:1000) 0.3 mg IM, diphenhydramine 50 mg IVP, hydrocortisone 100 mg IVP, and albuterol 2.5 mg inhalation (for bronchospasms). Vital signs should be monitored every 2 minutes until stable, then every 15 minutes until symptoms resolve. If cetuximab is restarted, restart the infusion rate at 25% of original rate for 30 minutes, then increase to 50% of infusion rate for the remainder of the infusion. The infusion rate should be permanently reduced by 50%.

Life-threatening/disabling (grade 4) HSRs consist of anaphylaxis, airway obstruction, shock, cardiac arrest, or prolonged hypotension.

Grade 4 HSRs require the immediate interruption of cetuximab therapy and permanent discontinuation from further treatment with cetuximab. Appropriate medical therapy including epinephrine, corticosteroids, intravenous antihistamines, bronchodilators, and oxygen should be available for use in the treatment of such reactions. Patients should be carefully observed until the complete resolution of all signs and symptoms.

### **6.3.4 Infusion Reaction Adverse Effects**

Severe infusion reactions (Grade 4) require the immediate interruption of cetuximab therapy and permanent discontinuation from further treatment. Appropriate medical therapy including epinephrine, corticosteroids, intravenous antihistamines, bronchodilators, and oxygen should be available for use in the treatment of such reactions. Patients should be carefully observed until the complete resolution of all signs and symptoms.

In prior clinical trials, mild to moderate infusion reactions were managed by slowing the infusion rate of cetuximab and by continued use of antihistamine pre-medications (e.g., diphenhydramine) in subsequent doses. If the patient experiences a moderate (Grade 3) infusion reaction, the infusion rate should be permanently reduced by 50%. For grade 1 or 2 reactions, additional doses of diphenhydramine or corticosteroids may be administered.

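### Section 6.3.4 labels a grade 3 cetuximab infusion reaction moderate and, unlike 6.3.3 at the same grade, neither orders the infusion stopped nor refers to 6.3.3

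*Combined protocol and SAP*

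**What the plan says.** Two neighbouring sections of the protocol cover acute reactions to cetuximab in Step Two, Cohort 2.

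Section 6.3.4 (Infusion Reaction Adverse Effects) begins with grade 4: "Severe infusion reactions (Grade 4) require the immediate interruption of cetuximab therapy and permanent discontinuation from further treatment". It then reports that in earlier trials "mild to moderate infusion reactions were managed by slowing the infusion rate of cetuximab and by continued use of antihistamine pre-medications" in later doses. The grade 3 instruction follows: "If the patient experiences a moderate (Grade 3) infusion reaction, the infusion rate should be permanently reduced by 50" per cent. For grades 1 and 2 it allows extra diphenhydramine or corticosteroids.

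Section 6.3.3 (Management of Hypersensitivity Reactions) uses different severity words. "Moderate (grade 2) HSRs consist of generalized pruritus, flushing, rash, back pain, dyspnea, hypotension, and rigors", and for these "The infusion should be stopped, and oxygen should be administered if the patient is experiencing dyspnea". At the next grade: "Severe (grade 3) HSRs are characterized by bronchospasm, generalized urticaria, hypotension, and angioedema. These HSRs should be managed by stopping the infusion and administering" fluids, epinephrine, diphenhydramine, hydrocortisone and, for bronchospasm, albuterol. If cetuximab is restarted after a grade 3 reaction, it runs at 25% of the original rate for 30 minutes and then at 50%, with a permanent 50% reduction. Grade 4 is called life-threatening or disabling and ends cetuximab.

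**The concern.** The same grade carries a different severity word and a different acute instruction, depending on which of two adjacent sections the site opens. At grade 3, 6.3.4 gives a rate reduction and nothing else: no order to stop, no acute treatment and no reference to 6.3.3.

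The label adds to the problem. The sentence about earlier trials says that mild to moderate reactions were handled by slowing the infusion. With moderate defined as grade 3, as 6.3.4 does, that sentence appears to include grade 3. With moderate defined as grade 2, as 6.3.3 does, it would not. The sentence is descriptive and is not an order. Even so, apart from the optional drugs at grades 1 and 2, it is the only text in 6.3.4 on handling a reaction below grade 4.

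What is at stake is the clarity of a patient-safety instruction during a cetuximab infusion.

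**Working it through.** No arithmetic applies. The check sets the two sections side by side by grade and then looks in the other cetuximab text for anything that closes the gap.

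| Grade | 6.3.3 label | 6.3.3 acute instruction | 6.3.4 label | 6.3.4 acute instruction | Lasting action |
|---|---|---|---|---|---|
| 2 | moderate | stop; treat; stepped restart | none attached to the number | optional extra diphenhydramine or corticosteroid | no lasting change in either |
| 3 | severe | stop; treat; restart at 25%, then 50% | moderate | none beyond the rate reduction | permanent 50% rate reduction in both |
| 4 | life-threatening/disabling | interrupt immediately | severe | interrupt immediately | permanent discontinuation in both |

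1. **Labels.** Moderate and severe each sit one grade higher in 6.3.4 than in 6.3.3. Section 6.3.1 also pairs severe with grade 3, for acneiform rash, so 6.3.4 is the odd one out.

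2. **Acute instruction at grade 3.** Section 6.3.3 stops the infusion; 6.3.4 has no stop order. This is the one grade where a defect is claimed.

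3. **Lasting action.** By grade number the two sections agree at grades 3 and 4.

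4. **Cross-references.** There are none in either direction.

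5. **Telling the two reaction types apart.** The protocol gives no rule. Three places suggest that they overlap. The sentence "Appropriate medical therapy including epinephrine, corticosteroids, intravenous antihistamines, bronchodilators, and oxygen should be available for use in the treatment of such reactions" appears in both sections. Diphenhydramine premedication is given in 8.3.8 to prevent hypersensitivity, and 6.3.4 mentions the same drug for infusion reactions. Section 8.3.10 directs monitoring for hypersensitivity reactions during the infusion. The overlap is an inference from these places; the protocol does not state it.

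6. **Cover elsewhere.** Bronchospasm, generalized urticaria, hypotension and angioedema at grade 3 fall under the 6.3.3 stop order. Section 6.3.6 interrupts cetuximab for acute-onset pulmonary symptoms of grade 2 or higher, or worsening ones, if they are not thought to be due to the cancer. Section 8.3.9 requires continuous observation for signs of anaphylaxis. None of these gives a general stop order for a grade 3 infusion reaction.

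What remains is a grade 3 event without those signs or symptoms, or one that has them but is handled under 6.3.4 alone because nothing there sends the reader to 6.3.3.

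**The case against.** The best defence is that the grade 3 sentence was never meant as acute guidance. Section 6.3 is about dose modifications and delays. The same permanent 50% reduction closes the grade 3 paragraph of 6.3.3, where it states the lasting consequence after the acute steps. The sentence just before it in 6.3.4 ends by referring to subsequent doses. Read this way, 6.3.4 sets only the later rate and leaves acute handling to 6.3.3 and clinical judgment. Each instruction also prints its grade number, and Appendix F grades toxicity by CTCAE version 4.0, so the number and not the adjective selects the rule.

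Much of this stands. The lasting-rate reading is plausible, and the label mismatch alone changes no lasting action. But 6.3.4 does not limit the sentence to later infusions, whereas 6.3.5 does so explicitly for drug fever. If the sentence does concern only later infusions, then 6.3.4 contains no acute instruction for grade 3 and no reference to the section that has one.

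A reader might infer three stronger things that the documents do not support:

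- **That 6.3.4 tells sites to keep infusing at grade 3.** It does not. The absence of a stop order is not an order to continue, and nothing there bars stopping.
- **That the gap runs across most grades, because 6.3.3 stops the infusion at all four and 6.3.4 only at grade 4.** That count is accurate as a description, but it takes in grades 1 and 2, where the lighter handling in 6.3.4 may be deliberate and no defect is shown.
- **That patients with serious reactions are left without a stop rule.** Sections 6.3.3 and 6.3.6 already stop or interrupt cetuximab for most serious presentations.

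**Conclusion.** The inconsistency is real, narrow and worth correcting. At grade 3, two adjacent safety sections use different severity words and give different acute instructions, and no text links them or separates the two kinds of reaction. It is more than a missing detail, because one event can meet two different written rules.

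Its reach is Cohort 2 during Step Two, at one grade. The documents state no reaction rate, so no patient count can be given. The primary endpoint is assessed at the end of Step One, before any cetuximab, and no endpoint, sample size or analysis depends on this text.

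The conclusion rests on one assumption: that a single bedside event could reasonably be filed under either heading. The protocol's own wording suggests this but does not say it.

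**What to change.** In 6.3.4:

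1. Relabel grade 3 as severe and grade 4 as life-threatening, in line with 6.3.3.
2. Replace the grade 3 sentence with: *For a severe (grade 3) infusion reaction, stop the infusion. If any grade 3 sign listed in 6.3.3 is present, manage and restart as 6.3.3 directs for grade 3. If cetuximab is restarted, reduce its rate by 50% permanently.*

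Leave the grade 1–2 text, the grade 4 actions and 6.3.5 as they are. Two wider changes are not advised. Sending every reaction with a hypersensitivity sign to 6.3.3, whatever its grade, would impose stop orders on many grade 1–2 reactions, since flushing, rash and fever are grade 1 signs there. It would also blur the separate rule for isolated drug fever in 6.3.5. Requiring the stepped restart when no 6.3.3 grade 3 sign is present would be a new clinical rule that no protocol text calls for.

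The cost is a short amendment and a brief interruption of the infusion for grade 3 reactions. No new drug, visit or data item is needed.

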### **6.3.5 Drug Fever Adverse Effects**

If a patient experiences isolated drug fever, subsequent pre-treatment with acetaminophen or a non-steroidal anti-inflammatory agent may be considered. If a patient experiences recurrent isolated drug fever following premedication and post-dosing with an appropriate antipyretic, the infusion rate for subsequent dosing should be 50% of previous rate.

